7.3 Randomization and Masking

7.3.1 Randomization Process and Sequence Generation

Randomization will be in a stratified and blocked fashion in a 1:1 ratio. Stratification factors will be by site, BMI (<30 or ≥ 30 kg/m²) and race (White or non-White [e.g. American Indian, Asian, Pacific Islander, Black]). Using stratified randomization helps balance the number of participants in each group for BMI and race, which are major determinants of vitamin D status and diabetes risk. The use of permuted blocks within each stratum will guarantee the balance between the two treatment arms during the course of randomization. The randomization will be administered by the Drug Distribution Center via the Interactive Web Response System.

Upon the participant's arrival at the randomization visit, the site research coordinator (or his/her approved designee) will log into the Interactive Web Response System and will enter the required stratification information (site, BMI and race). The system will use the stratification information to randomize the participant and assign a pill bottle (vitamin D or placebo). The research coordinator will then notify the site research pharmacist of the pill bottle number. The site pharmacist or designee will dispense a six-month supply of masked study pills to the research coordinator or nursing staff for distribution to participants.

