11. SAMPLE SIZE CALCULATIONS AND DATA ANALYSIS

11.1 Sample Size Calculation (Power Analysis)

The primary aim of D2d is to assess whether, in participants at risk for diabetes, oral daily vitamin D₃ supplementation will reduce the rate of progression to incident diabetes when compared to placebo.

The D2d study is designed as an event-driven trial to assure that the intended power to detect the hypothesized treatment effect (hazard ratio = 0.75, see below) is achieved irrespective of the event rate in the placebo arm.

The following considerations were used to determine the required number of events:

- 1) The primary study outcome is “time to confirmed diabetes”.
- 2) The primary hypothesis will be tested at a two-sided type 1 error rate (alpha) of 0.05.
- 3) If vitamin D therapy is superior to placebo, the hazard ratio will be 0.75 in the vitamin D arm as compared to the placebo arm.
- 4) The study is designed to have power of 90% to detect a hazard ratio of 0.75.

Based on these assumptions, the required number of events is 508²⁶⁴. To achieve the intended power, D2d will continue until 508 primary events have occurred.

Based on the following assumptions, it is estimated that the required (i.e. randomized) sample size will be 2,382 participants.

- 5) Participants will be recruited over a 2-year period (“accrual period”)
- 6) The expected study duration will be approximately 4 years plus an end-of-study visit over a period not to exceed three months.
- 7) The incidence rate of confirmed diabetes will be 10% per year (hazard rate = 0.1054) in the placebo group.
- 8) The loss-to-follow-up (i.e. going “off study”) rate will be up to 5% per year of follow-up (hazard rate = .0513).
- 9) If vitamin D therapy is superior to placebo, the hazard ratio will be 0.75 in the vitamin D arm as compared to the placebo group.

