4.3 Heterogeneity of treatment effect (HTE) analyses in relation to the primary outcome

4.3.1 Subgroup analyses

Heterogeneity of treatment effect to vitamin D supplementation for the primary outcome will be assessed in a standard approach by **subgroups** defined by the following **baseline** characteristics (i.e., at the time of randomization) will be conducted. The analysis plan follows widely recommended best practices: pre-specification of subgroups (motivated by biologically plausible hypotheses), interaction tests for heterogeneity of effects adjusted for multiple comparisons (see below), and inference for subgroup-specific effects only in the context of a statistically significant interaction.^{2-7 8,9}

- ✓ In general, subgroup analyses - even when pre-specified - are considered exploratory, as the power to detect heterogeneity of effects is generally low. Nevertheless, to adjust for multiple comparisons, we will use the Hochberg Sequential procedure¹⁰ when evaluating the significance (p-value for the interaction term) of each subgroup analysis. This procedure uses progressively more stringent statistical thresholds and is less rigid than the traditional Bonferroni correction method.
- Blood 25OHD concentration by a key Institute of Medicine cutoff (ng/mL) [justification: risk reduction will be larger among those with 25OHD < 20 ng/mL]
 - b. < 20
 - c. ≥ 20
- Race by self-reported definitions [justification: risk reduction will be larger among Blacks]
 - a. White
 - b. Black/African American
 - c. Other
- Glycemic risk by pre-diabetes criteria [justification: risk reduction will be larger among those who meet all three criteria and are considered at higher risk for diabetes]
 - a. Three criteria (FPG, A1c and 2hPG)
 - b. Two criteria (all other participants: FPG/A1c, FPG/2hPG, A1c/2hPG)
- BMI by standard clinical categories based on BMI (kg/m²) [justification: risk reduction will be larger among those with higher BMI]
 - a. Normal weight / Overweight < 30
 - b. Obese ≥ 30
- Glycemic risk by meeting 2hPG criterion for pre-diabetes [justification: differences in the underlying pathophysiology of people diagnosed by 2hPG may be important for the effect of vitamin D]
 - a. 2hPG (FPG/2hPG, A1c/2hPG, FPG/A1c/2hPG)
 - b. FPG/A1c only
- Ethnicity
 - a. Hispanic
 - b. Non-Hispanic
- Sex
 - a. Men
 - b. Women
- Waist circumference
 - a. < median value
 - b. ≥ median value

- Age
 - a. < median value
 - b. ≥ median value

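### The two glycemic-risk subgroup factors are nested and tested one at a time, so a significant interaction cannot be attributed to 2hPG or to the number of criteria

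*SAP*

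**What the plan says.** SAP 4.3.1 lists 11 baseline subgroup factors for the primary outcome. Two concern glycemic risk.

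- **Number of criteria.** One level is "Three criteria (FPG, A1c and 2hPG"); the other is all remaining participants, that is, any pair of criteria. The stated reason is that "risk reduction will be larger among those who meet all three criteria and are considered at higher risk for diabetes".
- **2hPG.** One level is "2hPG (FPG/2hPG, A1c/2hPG, FPG/A1c/2hPG"); the other is FPG/A1c only. The stated reason is that "differences in the underlying pathophysiology of people diagnosed by 2hPG may be important for the effect of vitamin D".

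The SAP calls subgroup analyses exploratory, adjusts the interaction p-values by the Hochberg procedure, and allows inference on subgroup-specific effects only when the interaction is significant. It does not mention the overlap between these two factors, fit them jointly, or adjust one for the other. Neither document gives the expected share of participants or events in any combination of criteria, or an assumed size of heterogeneity.

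**The concern.** The two factors carry different hypotheses, one about severity and one about mechanism, but they divide the same participants along overlapping lines. The 2hPG comparison sets a mixture of three-criteria and two-criteria participants against two-criteria participants only. If the SAP's own severity prediction is right, the two sides of the 2hPG comparison differ even when 2hPG plays no part of its own. The same happens in the other direction.

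At stake is the reading of a positive result. A significant 2hPG interaction could be reported as evidence on pathophysiology when the signal comes only from participants meeting all three criteria. The two tests are also positively correlated, so both could be significant and look like two separate findings. Hochberg deals with the number of tests and does nothing for attribution.

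**Working it through.** **1. The groups.** Protocol 5.1 requires at least two of the three criteria, so eligible participants fall into three exclusive groups:

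- A: all three criteria
- B: 2hPG plus one other (FPG/2hPG or A1c/2hPG)
- C: FPG/A1c only

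The number-of-criteria test is A versus B+C. The 2hPG test is A+B versus C. A lies wholly inside the 2hPG level and C wholly inside the two-criteria level. This follows from the definitions and needs no assumption. (SAP section 2 keeps 13 participants later found ineligible. If any of them missed the glycemic criterion, the three groups would not quite exhaust the cohort, but the nesting stands.)

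**2. Anchor to the plan's figure.** Inputs from Protocol 11.1 and 7.3.1: "The primary hypothesis will be tested at a two-sided type 1 error rate (alpha) of 0.05"; "The study is designed to have power of 90% to detect a hazard ratio of 0.75"; "Randomization will be in a stratified and blocked fashion in a 1:1 ratio". The Schoenfeld formula gives 4 × (1.960 + 1.282)² / (ln 0.75)² = 507.8, so 508, which agrees with "D2d will continue until 508 primary events have occurred".

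**3. Formulas.** Let eA, eB, eC be events per group and take the variance of each log HR as 4/events. Let r be the ratio of HRs between the affected and unaffected groups.

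- Only the number of criteria matters: the 2hPG contrast has mean ln(r) × eA/(eA+eB) and SE √(4/(eA+eB) + 4/eC).
- Only 2hPG matters: the three-versus-two contrast has mean ln(r) × eC/(eB+eC) and SE √(4/eA + 4/(eB+eC)).

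Neither mean is zero unless r = 1.

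**4. Two worked cases for the 2hPG test** (shares and HRs are assumptions; HR 0.60 in A, 0.85 in B and C, so r = 0.706 and ln r = -0.348):

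- Events 254/102/152 (50/20/30%): mean -0.348 × 254/356 = -0.249; SE √(4/356 + 4/152) = 0.194; |z| = 1.28; rejection about 25% at 0.05.
- Events 20/40/40%, that is 101.6/203.2/203.2: mean -0.348 × 1/3 = -0.116; SE √(4/304.8 + 4/203.2) = 0.181; |z| = 0.64; rejection 9.8% at 0.05 and 1.4% at the strictest Hochberg step, 0.05/11 = 0.0045.

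**5. Range.** 508 events. Unadjusted: eight mixes of participant shares (A 20-50%, B 10-60%, C 20-50%). Hochberg: three mixes and 11 tests, the other nine null and independent. In both, event risk in A is once or twice that of the others.

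| r | 2hPG test, only number matters: unadjusted | same, equal thirds and equal risk | same, Hochberg | Three-criteria test, only 2hPG matters: unadjusted | same, Hochberg |
|---|---|---|---|---|---|
| 1 | 5% | 5% | 0.4-0.5% | 5% | about 0.5% |
| 0.9 | 5.2-8.0% | 5.9% | not run | 5.2-7.8% | not run |
| 0.8 | 5.7-18.8% | 9.1% | 1.3-3.0% | 5.7-17.9% | 1.3-2.5% |
| 0.7 | 6.9-40% | 15.7% | 3.1-9.0% | 6.9-38% | 3.0-7.7% |
| 0.6 | 8.9-69% | 27.4% | 7.3-24% | 8.9-66% | 7.3-20% |

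The correlation between the two tests is 0.25-0.86 over the eight mixes. The Hochberg columns cover only the mixes tried; a small three-criteria share can go lower, as the 20/40/40 case shows.

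**6. What a joint model does.** With both treatment interactions in one Cox model, the 2hPG coefficient is B versus C and the number-of-criteria coefficient is A versus B. Patient-level simulation (2,382 participants, protocol hazards, equal thirds):

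- Only the number matters (HR 0.60 versus 0.86): B versus C rejects in 4.8%, against 15-19% for the planned 2hPG test.
- Only 2hPG matters (HR 0.69 versus 0.98): A versus B rejects in 4-5%, against 17-19% for the planned three-criteria test.

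**The case against.** The strongest reply is that nothing is wrong with the planned tests as tests. With a common HR they reject at their nominal rate. In the scenarios above, the HRs of the two compared groups truly differ, so a rejection is correct for the hypothesis tested. A reader might infer from the 25% case that the SAP inflates type I error. The documents do not support that reading: the figure depends on shares and heterogeneity they do not state, it ignores the Hochberg rule they do state, and it is not a false positive for A+B versus C. This part of the reply stands in full.

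Second, people meeting all three criteria do meet the 2hPG criterion, so the planned split is a legitimate marginal comparison. One-at-a-time testing is the usual convention, and the SAP claims no independence from severity. This stands for detecting heterogeneity. It does not stand for explaining it, because the stated rationale is mechanistic and here the overlap is built into the definitions.

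Third, a reader might infer that the 2hPG test should be replaced by a contrast within participants meeting exactly two criteria. That is not supported either.

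- The replacement drops the three-criteria participants, half of all events in the 50/20/30 case.
- It is less precise: SE √(4/102 + 4/152) = 0.256 instead of 0.194.
- Among two-criteria participants, having 2hPG means lacking FPG or A1c. Suppose only the A1c criterion modifies the effect (HR 0.60 versus 0.85) and half of group B lacks it. The contrast then has mean 0.348/2 = 0.174 and z = 0.68, and it rejects in about 10% at 0.05.

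**Conclusion.** The point holds as one of attribution. The nesting is exact, and nothing in the SAP separates the two factors, so neither interaction, if significant, can be assigned to its stated rationale. How often this would mislead cannot be fixed from the documents. At the unadjusted 0.05 level it ranges from near 5% to well above. Under the SAP's own Hochberg rule, the 2hPG test rejects in about 1-3% at an HR ratio of 0.8, 3-9% at 0.7 and 7-24% at 0.6 for the mixes tried, against about 0.5% per test with no heterogeneity. These figures rest on assumed shares, 508 events and variance 4/events. The analyses are exploratory, and the primary, secondary and safety analyses are untouched. This is a cheap improvement to what the subgroup analysis can conclude. It does not correct an invalid test.

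**What to change.** Keep both planned interaction tests, and the Hochberg count of 11, for detecting heterogeneity. Add to SAP 4.3.1:

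- One Cox model with treatment by a three-level factor: FPG/A1c only; 2hPG plus one other criterion; all three. Report the HR with confidence interval in each group and the ratios of HRs between groups.
- A rule that heterogeneity is attributed to 2hPG, or to the number of criteria, only if this model supports it. The relevant contrasts are 2hPG plus one versus FPG/A1c only, and all three versus 2hPG plus one.
- A caveat that, among participants meeting exactly two criteria, having 2hPG also means lacking FPG or A1c, so the first contrast is not a pure 2hPG effect.

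Do not substitute the within-two-criteria contrast for the planned 2hPG test.

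Cost: a few sentences and a little more analysis, with no new data. Detection power is unchanged because both planned p-values stay. The attribution contrasts are imprecise. In the equal-thirds simulation, unadjusted power for the factor that truly matters is about 38-39% (all three versus 2hPG plus one) instead of 47-53%, and 31-39% (2hPG plus one versus FPG/A1c only) instead of 43-51%. Often the honest conclusion will be that the source of any heterogeneity cannot be determined.

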5 SECONDARY ANALYSES

Effect of vitamin D supplementation on secondary outcomes (**as continuous variables**) will be based on a linear mixed model and account for within subject correlation in repeated measurements over time. The overall mean difference between vitamin D and placebo groups for these analyses will be tested using the nominal 0.05 type 1 error rate *without adjustment for multiple comparisons*.^{11,12}

Some of these analyses (e.g., insulin secretion, cardiovascular risk factors) will not be presented in the main manuscript but in separate publications.

5.1 Related to the primary outcome (i.e., diabetes).

Change from baseline in:

- HbA1c, FPG and 2hPG
- Insulin secretion, sensitivity and disposition index. (indices derived from the OGTT).

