Data Monitoring Plan – Methods for interim analysis of accumulating data will be reviewed and approved by the D2d DSMB, which will regularly review accumulating safety and efficacy data to assure that continuation of the study remains scientifically and ethically appropriate. As a specific part of this monitoring activity, a single formal interim analysis of the accumulating primary endpoint data will take place when 70% of the expected events have accrued. The stopping boundary for the interim analysis will be based on the Peto-Haybittle approach.^{279,280} With this stopping boundary, the nominal P value representing statistical significance will be 0.001, corresponding to a Z score of 3.09.

The D2d coordinating center will prepare the reports on behalf of the DSMB, whose members will review the data and advise the sponsor (NIDDK) whether (1) there is evidence that the intervention is clearly better or worse than placebo in relation to the primary outcome, and (2) the DSMB recommends a change in the study plan based on safety considerations.

Seasonal and Geographic Variability – Given that the cohort will be recruited at a constant rate throughout the calendar year and outcomes will be determined every 6 months, the potential for seasonal variability confounding the association between vitamin D supplementation and outcomes is low. We will test this assumption in the analyses, and if needed, we will adjust for the month of the year at entry into the study. All analyses will adjust for site, as routinely done in multicenter studies, which will also approximate latitude at each of the participating sites. Given the age group, we anticipate few participants moving residence during the study.

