1 OVERVIEW & ADMINISTRATIVE INFORMATION

The present version 2 of the Statistical Analysis Plan (SAP) corresponds to version 1.9 of the protocol and associated Manual of Procedures.

The Statistical Analysis Plan (SAP) includes statistical hypotheses, outcome measures, methods for the primary outcome analysis and subgroup analyses. The SAP follows the outline and general principles outlined in the Data Analysis Plan section of the protocol; however, the SAP provides more detail compared to the protocol while previously proposed analyses that are of questionable value have been removed.

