3.2.1 Secondary outcomes – related to the primary outcome: continuous variables

- HbA1c (measured at baseline, semi-annually)
- FPG (baseline and semi-annually)
- 2hPG (baseline and annually)
- Insulin secretion, Insulin sensitivity and Disposition Index (indices from OGTT; baseline and annually)

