3.2.2 Secondary outcomes – independent of the primary outcome: continuous variables

- Blood pressure (baseline and semi-annually)
- Cardiovascular risk factors: cholesterol profile, C-reactive protein, urine albumin excretion (baseline, M12 and M24)
- Atherosclerotic Cardiovascular Disease (ASCVD) ACC/AHA composite risk score (baseline, M12, M24)

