3.3 Explanatory outcome: continuous variable

- 25OHD concentration (baseline, M12 and M24)

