4 PRIMARY ANALYSIS & SUPPORTING ANALYSES

The *primary analysis* of D2d will assess whether, in participants with pre-diabetes, oral daily vitamin D₃ supplementation reduces the rate of progression from pre-diabetes to incident diabetes (=primary outcome).

All randomized participants are included in the analysis. Kaplan-Meier estimates of “time to confirmed diabetes” distributions will be calculated for each treatment group. The log-rank test will then be used to perform an unadjusted comparison of the time-to-event distributions in the two treatment groups. Follow-up of participants who do not complete the study (e.g. withdrew) will be "censored" on the date of their last follow-up encounter (see below). Cox proportional hazard modeling will be used to compare the risk of incident diabetes in the two groups.¹ The model will include an indicator for the randomized intervention as its main predictor variable. Clinical site at randomization will be a stratifying factor. The baseline variables (BMI, race, as entered in SPIRS) used to stratify the randomization will also be included as stratifying factors.

The p-value from the primary analysis will be based on the chi-square statistic from a likelihood ratio test obtained from proportional hazards models with and without the term for intervention arm. Comparisons of the intervention groups will be performed per the ITT principle, with all randomized participants grouped per their intervention assignment at randomization, regardless of adherence. Unless otherwise specified, p values will be two tailed, and values below 0.05 are considered statistically significant.

Definitions of follow-up time and censoring. Follow-up time for the primary outcome will be censored at the date of the *last assessment for diabetes with data in the electronic data capture system as of the cutoff date (as defined in the Manual of Procedures – section 20)*.

Censoring for participants *with diabetes* occurs at the date of the diabetes event, as shown in the *Diabetes Outcome* form in EDC. Specifically,

- If the diagnosis of diabetes is made within the study (i.e., using results by the Central Laboratory), the date of onset of diabetes is defined as the date of the first diagnostic glycemc value.
- If the diagnosis of diabetes is made outside of study (i.e., adjudicated), the date of onset of diabetes is determined during the adjudication process.

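### SAP section 5 does not name a baseline term or the BMI and race strata in its mixed models for change from baseline; naming them costs nothing and may sharpen the secondary estimates

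*SAP*

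**What the plan says.** SAP section 5 covers HbA1c, FPG, 2hPG, the OGTT indices, blood pressure, cardiovascular risk factors, the ASCVD score and 25OHD. The outcome is change from baseline, and the analysis "will be based on a linear mixed model and account for within subject correlation in repeated measurements over time". An overall mean difference between arms is tested at a nominal 0.05 without multiplicity adjustment. No fixed effects are listed. The only covariate mentioned is a three-category race interaction test for blood pressure in section 5.2.

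Elsewhere the documents do name such terms:

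- SAP section 4, for the primary Cox model: "The baseline variables (BMI, race, as entered in SPIRS) used to stratify the randomization will also be included as stratifying factors".
- Protocol section 11.2 forces baseline glycaemia, 25OHD, BMI and race into the adjusted Cox model, again for the primary outcome.
- Protocol section 7.3.1 stratifies by site, BMI and race, and says that this balances "BMI and race, which are major determinants of vitamin D status and diabetes risk".
- Site is promised generally in Protocol section 11.2: "All analyses will adjust for site, as routinely done in multicenter studies". SAP section 1 carries this over: "The SAP follows the outline and general principles outlined in the Data Analysis Plan section of the protocol". Site is therefore not a gap; SAP section 5 only fails to repeat it.

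**The concern.** A mixed model for change from baseline can be fitted in at least four ways, and SAP section 5 neither states nor rules out any of them:

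- (a) the change score as response, with no baseline term;
- (b) baseline as part of the response, with a separate baseline mean in each arm;
- (c) baseline as part of the response, with one baseline mean common to both arms;
- (d) baseline as a covariate.

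Under randomisation all four are unbiased, but (a) and (b) are less precise than (c) and (d). The section's wording, taken literally, is (a). Two analysts could both follow the SAP and report different standard errors and p-values from the same data. Some of these outcomes are destined for separate publications, where different people may fit the models.

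The strata raise a smaller matter. The randomisation was stratified on BMI and race, and an analysis that ignores strata related to the outcome tends to report too large a standard error.

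**Working it through.** **Plan's own figure.** The documents give no SD, correlation, sample size or power for any continuous secondary outcome, so there is nothing to reproduce on this point. The primary target of 508 events does reproduce, as 4 × (1.960 + 1.282)² / (ln 0.75)² ≈ 508, but it does not depend on these models.

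**Inputs.** Number of follow-ups k: two for 25OHD and the cardiovascular factors (M12 and M24; SAP 3.2.2, 3.3 and the note in 5.2). About six for semi-annual blood pressure over the roughly 3-year mean follow-up (SAP 3.2.2; Protocol 4.1). Correlation rho between a participant's measurements: *not given*; assumed 0.5, 0.7, 0.9, equal at all visits, with equal variances and an unrestricted baseline.

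**Baseline term.** Per-participant variance of the mean over k follow-ups, unit SD:

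- change score: Vc = (1 + (k−1)rho)/k + 1 − 2rho = (k+1)(1−rho)/k
- baseline-adjusted: Va = (1 + (k−1)rho)/k − rho² = (1−rho)(1+k·rho)/k
- difference: Vc − Va = (1−rho)², never negative
- ratio: Vc/Va = (k+1)/(1+k·rho)

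| k | rho | Vc | Va | Vc/Va | SE ratio |
|---|---|---|---|---|---|
| 2 | 0.5 | 0.750 | 0.500 | 1.50 | 1.225 |
| 2 | 0.7 | 0.450 | 0.360 | 1.25 | 1.118 |
| 2 | 0.9 | 0.150 | 0.140 | 1.07 | 1.035 |
| 6 | 0.5 | 0.583 | 0.333 | 1.75 | 1.323 |
| 6 | 0.7 | 0.350 | 0.260 | 1.35 | 1.160 |
| 6 | 0.9 | 0.117 | 0.107 | 1.09 | 1.046 |

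At k = 2, an effect with 80% power under the unadjusted change score has about 93%, 88% or 83% power with baseline adjustment. The k = 6 rows assume complete semi-annual values. Protocol section 7.4 lets some of those visits take place by phone, so they are an upper guide.

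**Simulation of the four forms** (n = 2,000, 4,000 runs, true effect 0.1 SD). Variance relative to (d) at k = 2 was 1.51, 1.24 and 1.06 for (a), identical for (b), and 0.999 throughout for (c). Mean estimates were 0.099 to 0.100 for all four.

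**Strata, analytically.** Suppose the strata explain a share s of outcome variance at every visit, and put rho_w = (rho−s)/(1−s). With baseline already in, the reported SE without strata divided by that with strata is √[(1−rho)(1+k·rho) / ((1−s)(1−rho_w)(1+k·rho_w))]. For k = 2, rho 0.5, s 0.10: rho_w = 0.444, and √[1.000/0.944] = 1.029. Over rho 0.5 to 0.9 and k = 2 the ratio is 1.001–1.005 (s = 0.02), 1.002–1.013 (s = 0.05) and 1.004–1.029 (s = 0.10). For a change score a constant stratum effect cancels and the ratio is 1. The values of s are assumptions.

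**Strata, by simulation** (stratified 1:1, N = 2,024, k = 2, 1,500 runs per setting, baseline in the model).

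- The actual variance of the estimate changed by at most 0.006 (on a scale where the change score is 1) when strata were added.
- In the six settings where the strata also predicted change, the reported variance without and with strata ran from 0.833 against 0.773 (SE ratio √1.078 = 1.038) to 0.963 against 0.823 (SE ratio √1.170 = 1.082).
- Type I error in those settings was 0.031–0.043 without strata and 0.046–0.053 with them. The Monte Carlo error of each figure is about √(0.05 × 0.95/1,500) = 0.006, but the direction was the same in all six.

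**The case against.** **No loss is shown.** SAP sections 3.2.1 and 3.2.2 list baseline among the measurement times, so form (c) is a natural reading, and under it only wording is missing. This stands. A reader might infer that the secondary analyses will in fact lose precision; the documents support only that the model is unspecified and that its literal reading is the less precise one.

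**The sizes cover the less central outcomes.** This also stands. Entry criteria truncate baseline FPG, HbA1c and 2hPG (Protocol 5.1 and 5.2), so the equal-variance formula does not apply to them, and nothing in the documents sizes the OGTT indices. For 25OHD the arm contrast should be so large that a wider SE changes no conclusion. For example, assume a 10 ng/mL difference, SD 12 and 500 per arm (none given): z = 10/(12√(2/500)) ≈ 13, and about 11 with an SE 22% larger.

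**A baseline term and strata alone would not fix the model.** Visit, arm-by-visit and the meaning of the overall mean difference would still be open. That is right, and the fix includes them.

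**These are secondary analyses meant to help interpret the primary result.** True, and the point is graded accordingly. Several outcomes are nevertheless tested at a nominal 0.05, and a sentence or two settles how.

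**Conclusion.** The point holds as a free improvement to the secondary analyses. Read literally, SAP section 5 gives unbiased estimates with a standard error about 22%, 12% or 3.5% larger than necessary at rho 0.5, 0.7 or 0.9 with two follow-ups. These figures rest on assumed, equal correlations and variances; the gain is zero if a common baseline mean or a baseline covariate is already meant.

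A reader might go further and say that nearly all of the gain comes from the baseline term. The documents do not support any fixed share: it depends on rho and on how much variance the strata explain. If the strata are credited with the residual variance that they explain after baseline, the baseline share at two follow-ups and rho 0.9 is 88% when they explain 1% of it, but 59% when they explain 5%. Protocol section 7.3.1 regards BMI and race as major determinants of vitamin D status, so a small stratum effect is least safe to assume for 25OHD.

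Nor should the strata be presented as a gain in true precision, since randomisation already balances them. Their role is to bring the reported standard error and the test back to nominal.

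The primary Cox analysis, its type I error and the event target are untouched.

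**What to change.** In SAP section 5, state that every mixed model includes:

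- the baseline value as a covariate, or baseline in the response with a mean constrained equal across arms;
- the BMI and race strata as randomised, as in SAP section 4;
- site, restating the commitment in Protocol section 11.2;
- visit, arm and arm-by-visit.

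Define the overall mean difference as the average of the arm differences over the follow-up visits.

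The cost is a few sentences and the matching model statements. Baseline values and strata are already collected; no visit, sample or assay is added.
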